APPENDIX

- I Patient information sheet and informed consent**
- II Knee society score evaluation (KSS)**
- III WOMAC patient questionnaire,
EQ-5D patient questionnaire,
Visual Analogue Scale (VAS) as patient questionnaire to measure results of chair raise test**
- IV and V Product Information**

SCORPIO PS Vs SCORPIO NRG PS

Comparative Investigation of Function

STUDY DESIGN SUMMARY

- **Surveillance design:** Single-centre, prospective, randomized comparative study.
- **Objectives:** To compare the average Range of Motion and Chair Raise achievement ratios. All complications will be documented.
- **Regulatory status:** Scorpio PS: CE Number: 0050
Scorpio PS NRG: CE Number :0086
- **Number of subjects to be enrolled:** All consecutive Scorpio patients are included until a group size of 88 is reached.
- **Clinical evaluations:** Chair raise test, Stair climb test, WOMAC patient self-evaluation, EQ-5D patient questionnaire. Standard clinical, functional and pain parameters (Knee Society Score), pre-operatively and post-operatively. All per- and post-op complications.

SCORPIO PS Vs SCORPIO NRG PS

Comparative Investigation of Function

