2.2 Randomisation procedure

The randomisation procedure will be executed by the scientific researcher with the computer programme randomizer. After defining group size and the amount of subgroups, a list will be given with patient inclusion number and the prosthesis that has to be used. The scientific researcher will make envelopes with a form inside which mentions the patient inclusion number and type of prosthesis that has to be implanted. On the day of surgery a randomisation envelope will be opened.

If the surgeon notices during the operation that the study prosthesis is not suitable for the patient's anatomy, he will exclude the patient from the study and will place a suitable prosthesis.

The following criteria determine deviation from the randomisation procedure:

- Bone stock quality far less than expected by X-ray (patient will receive long stem revision prosthesis and will be excluded from the study)
- Fracture or fissure in tibial plateau threatening prosthesis stability (patient will receive long stem revision prosthesis and will be excluded from the study)

This will be mentioned in the CRF as a complication and the patient will be excluded from further participation.

The patient will not be informed which prosthesis he/she has received.

All study related operations will be performed under computer navigation.

2.3 post-operative evaluations

After surgery the patient will be evaluated at fixed follow up moments (Table 2 page 8). At each follow up moment a KSS evaluation, a chair raise and stair climb test combined with VAS pain score will be done. Also patient questionnaires (WOMAC, EQ-5D) will be done and X-rays will be taken.

The KSS score consists of a knee score (pain, range of motion en function of the prosthesis) and a function score (walking, stair climbing, use of support). To compare this KSS between

the different follow up moments the improvement can be measured. The stair climb and chair raise test will be executed in the same way at every follow up. The pain during these two activities measured with a VAS will be compared between the follow up moments.

All clinical measurements will be done by the clinical researcher. Specific knee clinical evaluations have to be done by a knee specialist to make sure that everything is done correctly.

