3 OBJECTIVES

The primary objective is to compare the maximum flexion, both passive and active at every clinical follow-up time point up till 5 years postoperative, measured with a large goniometer. Our primary hypothesis is that the Scorpio NRG PS knee prosthesis has an average flexion of at least 7 degrees higher than the Scorpio PS knee prosthesis. Secondary objectives are to assess the complications, Chair raise test outcomes, knee pain (VAS) and surgery time. The secondary hypothesis is that there is no difference in complications and pain during the stair climb and chair raise test between the Scorpio NRG PS and the Scorpio PS. So more flexion does not result in more anterior knee pain. Also, the validity of computer navigated measurements and the relation between patella tilting and post-operative pain will be evaluated.

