14.1 Statistical Analysis

There will be summaries and comparisons presented according to:

- Demographic and pre-operative assessments
- Operative assessments
- Post-operative pain and function assessments
- Chair raise and stair climb assessment
- Patella-tracking assessment
- Adverse events
- General complications
- Local complications
- Device-related complications
- Revisions/removals

Descriptive statistics will be used like frequency and percent distributions and will be presented in tabular form for categorical variables. The mean, standard deviation, minimum and maximum values will be presented for quantitative variables. Students T-test will be used to compare variables between groups and various time points.

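### Section 14.1 names only Student's t-test, leaving yes/no outcomes and within-patient comparisons between visits without a suitable stated method

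*Combined protocol and SAP*

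**What the plan says.** Section 14.1 opens its list of outcome categories with "There will be summaries and comparisons presented according to". The list includes chair raise and stair climb, adverse events, general and local complications, "Device-related complications", and revisions or removals. Description is split by variable type. For categorical data: "Descriptive statistics will be used like frequency and percent distributions and will be presented in tabular form for categorical variables". For the rest: "The mean, standard deviation, minimum and maximum values will be presented for quantitative variables". One sentence on inference follows: "Students T-test will be used to compare variables between groups and various time points". It does not say which variables it covers or whether comparisons between time points are paired.

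Other sections rely on these comparisons. The Study Design Summary gives the objective as "To compare the average Range of Motion and Chair Raise achievement ratios". Section 3 states: "The secondary hypothesis is that there is no difference in complications and pain during the stair climb and chair raise test". Section 2.3, on stair climbing and chair raise, adds: "The pain during these two activities measured with a VAS will be compared between the follow up moments".

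**The concern.** Two kinds of comparison that the plan promises do not fit the single test it names.

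- **Yes/no outcomes.** Complications, revisions and, as the summary words it, chair-raise achievement are proportions. A test of means on sparse 0/1 data can cross the 5% line where an exact test does not. It also yields nothing when no events occur. A hypothesis of no difference needs an estimate with an interval, because a non-significant p-value does not show that the groups are alike.
- **Repeated visits.** Pain and function are measured on the same patients before surgery and at six post-operative visits (Table 2). Comparing two visits as if they were independent samples discards the within-patient correlation.

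At stake is how safety, chair raise and change over time are reported. If the method stays open, it can be chosen after the data are seen.

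**Working it through.** **1. The plan's own figure.** Section 6.1 gives a difference of 7 degrees, SD 11, 80% power and two-sided alpha 0.05. The two-sample t calculation gives 39.75, so 40 per group, and power at 40 is 80.3%. Adding 10%: 80 × 1.10 = 88. The plan's figures reproduce, and a t-test suits the flexion comparison between groups at one visit.

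**2. Yes/no outcomes, individual results.** The documents give no event rates, so counts and rates below are illustrative. For 0 v 4 events at 40 per arm:

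- t-test: pooled variance = (4 × 0.9)/78 = 0.04615; t = 0.10/√(0.04615 × 2/40) = 2.08 on 78 degrees of freedom; p = 0.041.
- Fisher: 2 × C(40,4)/C(80,4) = 0.116.

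| Events (40 per arm) | t-test | Uncorrected chi-square | Fisher |
|---|---|---|---|
| 0 v 4 | 0.041 | 0.040 | 0.116 |
| 0 v 5 | 0.021 | 0.021 | 0.055 |
| 1 v 6 | 0.049 | 0.048 | 0.108 |

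At 44 per arm (88/2) each pair of t-test and Fisher results still falls on opposite sides of 0.05.

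**3. Yes/no outcomes, long-run error.** Rejection rate with no true difference at nominal 5%, by exact binomial enumeration at 40 per arm:

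| Assumed event rate | t-test | Chi-square | Fisher |
|---|---|---|---|
| 2% | 0.007 | 0.007 | 0.000 |
| 5% | 0.043 | 0.043 | 0.004 |
| 10% | 0.059 | 0.059 | 0.017 |
| 20% | 0.051 | 0.051 | 0.028 |
| 50% | 0.057 | 0.057 | 0.033 |

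Over these rates the t-test's true size runs from 0.7% to 5.9%, the same as chi-square. At a 2% rate the chance of no events in either arm is 0.98^80 = 0.20, and the t statistic then cannot be computed.

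**4. What an interval would add.** The Newcombe interval combines the Wilson limits of each arm.

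- *0 v 0 at 40 per arm:* the Wilson upper limit is z²/(n + z²) = 3.84/43.84 = 0.088, so the risk difference is 0 with a 95% interval of ±8.8 percentage points.
- *0 v 4:* the Wilson limits are 0 to 0.0876 and 0.0396 to 0.2305. Lower limit: 0.10 − √[(0.10 − 0.0396)² + 0.0876²] = −0.006. Upper limit: 0.10 + (0.2305 − 0.10) = 0.231. The result is 10 points, interval −0.6 to 23.1.

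Either result shows how large a difference remains possible. The t-test p-value does not.

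**5. Comparisons between visits.** With equal SDs and correlation r, the unpaired standard error divided by the paired one is 1/√(1 − r). Correlations are assumed because none is given. Error and power come from 20,000 simulated trials with 40 patients and two visits, for a 5-degree change with SD 11.

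| r | SE ratio | Type I error, unpaired | Power, unpaired | Power, paired |
|---|---|---|---|---|
| 0.3 | 1.20 | 0.020 | 52% | 66% |
| 0.5 | 1.41 | 0.007 | 53% | 80% |
| 0.7 | 1.83 | 0.001 | 53% | 95% |

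Run in paired form, the type I error is about 0.05 throughout. Only a negative correlation reverses the direction: at r = −0.2 the unpaired test rejects 7.5% of the time.

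**The case against.** The strongest reply is that Section 14.1 is incomplete rather than wrong. It separates categorical from quantitative variables, and the t-test sentence directly follows the quantitative one. It can be read as applying to quantitative variables only, with categorical ones tabulated and no test named. That reading is fair, but the promised comparisons of complications and revisions would then have no method at all, and the same repair is needed.

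Several stronger inferences are tempting, and the documents do not support them:

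- *That the plan prescribes a t-test for yes/no data.* The word for what is compared is unqualified, so this is possible, but it is never stated. Chair raise also carries a 0 to 10 pain score, which is quantitative, and the achievement ratio is not defined beyond the summary.
- *That the p-values would be wrong.* The size figures above are close to nominal or below it. The sparse examples partly reflect how conservative Fisher's test is.
- *That visits will be compared as independent samples.* Pairing is unspecified, and the paired t-test is a form of Student's test that is valid for two visits. The unpaired form, with positive correlation, loses power but does not create false positives.
- *That reported error bars would be distorted.* No standard errors or confidence intervals are planned.
- *That the primary comparison fails.* It is a difference in means between groups.

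One part of the objection changes the remedy. Mandating Fisher's test would reduce the chance of seeing a real safety difference. At 40 per arm, with assumed true rates of 5% v 20%, power is 41% by Fisher and 57% by t-test; at 2% v 15% it is 36% v 63%. When the stated hypothesis is no difference, a conservative test favours it.

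**Conclusion.** The point holds as a gap in specification with limited but real consequences. As written, one test serves every comparison, and no suitable method is stated for sparse yes/no outcomes or for repeated visits in the same patients. The consequences are a possible change of significance in individual low-count comparisons, no result where no events occur, no estimate to support the hypothesis on complications, and, if visits are compared unpaired, a standard error 1.20 to 1.83 times what it need be. Those sizes rest on assumed event counts and on assumed correlations of 0.3 to 0.7. For non-sparse binary data the t-test and the uncorrected chi-square test nearly coincide. The flexion comparison between groups at a single visit and its sample size stand. The case for change rests on the risk-difference interval and the within-patient modelling, not on preferring Fisher's test.

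**What to change.** Replace the t-test sentence in Section 14.1 with text to this effect:

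- Continuous outcomes between groups at a given visit: Student's t-test.
- Yes/no outcomes (complications, revisions, chair raise achieved): number and percentage per group, and the risk difference with a Newcombe 95% confidence interval. The accompanying test is chi-square, or an exact test when counts are sparse, with the rule for switching stated in advance. Define chair-raise achievement.
- Comparisons between visits: within-patient contrasts from one repeated-measures model containing all visits.

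The conclusion on complications should be drawn from the interval, not from a non-significant p-value.

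The cost is one paragraph and slightly more analysis work in standard software, with no added patients or data. The drawback is that an exact test, where used, has less power to detect a real safety difference, which is the reason to let the interval lead.

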15 PUBLICATION OF RESULTS

For this study, as a single-centre Stryker Initiated Study, the following shall apply:

Ownership of data

- Study data owned, managed and analysed by Stryker SA

Publication plan

- Collectively defined and agreed by Stryker and Principle Investigator before study start
- Analysis timelines
- Covers Journals, Congresses and according timelines
- **2 year after completion of follow-up we plan to submit an abstract with preliminary findings to ORS and EFORT and the National Dutch Orthopaedic Association meeting.**
- **We plan to submit a two year data paper to either JBJS Br or Acta Orthopaedica depending on the data outcome and its relevance to the orthopaedic research community.**
- **We will submit a 5 year follow-up paper to either JBJS Br or Acta Orthopaedica depending on the data outcome and its relevance to the orthopaedic research community. This data will also be presented at orthopaedic conferences such as EFORT, ORS and the National Dutch Orthopaedic Association meeting.**

Authorship

- Number and Order to be agreed by Stryker and Principle investigator (according to requirements of intended Journals)
- If required by the intended Journal, the study will be registered publicly on the required internet site. (Release of information is limited to serve the aforementioned purpose, taking into consideration that scientific methods and protection of intellectual property of the sponsor and the Investigators).

Later publications

- Any publication proposals containing study data (including presentation of the data at any public event) after the general publication has been published in a peer review journal, shall be submitted to Stryker for review and acknowledgement, min. 30 days in advance.

16 RISK BENEFIT ANALYSIS

16.1 Risk

The Scorpio PS knee prosthesis is standard used for total knee arthroplasties in the AZM. During the 10 years experience with the Scorpio PS no additional complications have been seen. The Scorpio NRG PS has evolved from the the Scorpio PS. In basis both prostheses are

the same, only the tibial insert has changed and the femoral component has a slightly different shape. No additional risks for the use of the Scorpio NRG knee prosthesis are expected but still need to be proven. As in any surgical procedure, certain risks are associated with total knee arthroplasty. These risks include but are not limited to: anaesthetic and post-anaesthetic reactions (such as hyperaemia), allergic reactions to prophylactic antibiotics or blood transfusions, damage to blood vessels or nerves, patella, femoral or tibial fractures during implantation, perforation of the cortical wall, or death. Post-operatively, a patient may experience thrombophlebitis, pulmonary embolus, dislocation, pain, limp, component loosening, or the need for additional surgery.

16.2 Minimization of Risks

Pre-clinical, clinical, and mechanical testing of the Stryker Scorpio TKA designs indicate that the above mentioned risks should not occur at a rate greater than that for any other type of TKA systems reported in the literature.

16.3 Benefit

Patient benefits should include relief of pain and therefore increase in functional capabilities, in addition to better assessment of the effect of the implant design and materials on functional and radiographic performance and bone remodelling around the implant. This will increase the current scientific body of knowledge concerning TKA and possibly leading to improved implant designs.

17 ETHICAL CONSIDERATIONS

Informed Consent

Prior to entry into the Surveillance the investigator (or nominated representative) will give the patient written (in native language of the patient) and verbal explanation of the nature of the study to an appropriate level of detail. The patient must give a written consent to participate in the study. Patients are invited to sign and date the consent form, indicating their consent for enrolment (Investigators may not date the consent form on the patient's behalf).

The investigator (or nominated representative) will also sign and date the Consent Form to indicate that the purpose, risks and benefits of the study were explained to the patient and their signature witnessed. The original signed Consent Form will be filed at the Investigational site.

Patients are free to withdraw from the Investigation at any time and are under no obligation to provide a reason for doing so. A clinical trial insurance and a liability insurance is arranged. An independent orthopaedic surgeon is appointed who is fully informed about this study but does not participate in the study.

Patients can, at any time, receive information about his/ her results.

The study will be performed according to the declaration of Helsinki, wet medisch-wetenschappelijk onderzoek met mensen and guidelines CCMO.

Stryker's local CRA will provide the MEC azM/UM with the following reports:

- An annual progress report
- An end-report, sent within 8 weeks after completion of the study
- An end-report containing the results and conclusions, sent within 1 year after completion of the study

Personal data protection

Stryker Europe affirms and upholds the principle of the patient rights to protection against invasion of privacy. All data recorded in the CRFs or used for further evaluation are coded by patient study number. Identification is restricted to authorized persons. In all data analyses the identity of patients will remain anonymous. Anonymous patient data may be stored and electronically processed by Stryker Europe for the purpose of scientific evaluation and may be forwarded to a company and/or an authority located in- and outside Europe for registration and/or marketing purposes. Only authorized representatives of Stryker Europe and health authorities will have allowed access to personal medical records for the sole purpose of checking the accuracy of data collected in the trial.

